# 9.2. Baseline (Day-1 or Day 0)

Baseline assessments may be completed the day before or day of study drug administration, before the XT-150 injection.

- Brief physical exam, including examination of the injection site.
- Obtain any changes from the complete medical history.
- Record any changes or updates in medications, including pain medications (prescription and non-prescription) and therapies (e.g., physical therapy, acupuncture) administered since Screening visit.
- Efficacy assessments
  - VAS score. Verify VAS ≥50.
  - Oswestry Disability Index
  - International Physical Activity Questionnaire (IPAQ) short form
  - SF12
  - Record participant's response to the OA question: "Considering all the ways that facet pain, the pain that brought you into this study, affects you, how are you doing today?" on a scale of 1 to 5, 1 being very good (asymptomatic and no limitation of normal activities) to 5, very poor (very severe, intolerable symptoms and inability to carry out normal activities)
- Clinical assessments

- Measure vital signs (temperature and the site collected [oral, rectal, temporal, or tympanic], heart rate, blood pressure, and respiratory rate)
- Laboratory assessments
  - Obtain serum for analysis of IL-10 protein and anti-IL-10 antibodies
  - Obtain whole blood for plasmid DNA analysis
- Confirm participant qualification by inclusion/exclusion criteria. Enroll participant prior to dosing

## 9.3. Day 0

- Before administration of study drug:
  - Confirm that all study criteria are met (inclusion and exclusion)
  - Brief physical exam
  - Injection site examination
  - Record any ongoing medical observations that occurred since Screening visit
  - Record any new AEs since Screening
  - Record any concomitant medications since Screening including prescription, OTC and herbal medications. Ensure no excluded medications.
- Administer study drug (see Section 8 for details on preparation)
  - Aseptic techniques will be used in the preparation and administration of XT-150
  - Injections will be guided by ultrasound, fluoroscopy or equivalent visualization
  - All injections of study drug must be performed by a specialist who is qualified, trained, and experienced to perform intra-articular injections to the Facet joint.
  - Examine injection site for infections or reactions
- Clinical assessments
  - Monitor Participant for approximately for 4 hours for signs of study drug reaction.

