## 10.2. Adverse Events

Medical history will be collected for all participants at the time of informed consent. After consent, all adverse events (AEs)/serious adverse events (SAEs) will be collected through the last study visit on Day 270. All AEs/SAEs that occur during or after the time of study drug treatment will be considered treatment-emergent AEs (TEAEs). The Investigator will assess all AEs and SAEs and will record the following information on the appropriate CRF page and SAE Report Form (as applicable):

- Event term
- Date of onset
- Date of resolution or stabilization
- Severity
- Relationship to study drug
- Action taken with study medication

Medically indicated laboratory tests (emergency or unscheduled tests) should be conducted at the local laboratory. The Investigator should employ best medical judgment in determining how to manage AEs and SAEs. Any questions regarding AE or SAE management should be directed to the Medical Monitor.

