# 14.4. Safety Analysis

All participants who receive any amount of study drug (Safety Population) will be included in the safety analyses.

[figure not shown]
Safety will be evaluated by presenting summaries of AEs, clinical laboratory tests, and vital signs. Safety variables will be tabulated by treatment group.

[figure not shown]
Adverse events will be graded using the CTCAE v5.0 and will be coded using the Medical Dictionary of Regulatory Affairs (MedDRA®), Version 24 or higher. AEs will be collected for each participant from the signing of the informed consent through the last study visit on Day 180.

A treatment-emergent adverse event (TEAE) is defined as an AE that occurs during or after study drug administration. The incidence of TEAEs will be presented by system organ class (SOC) and preferred term (PT), by SOC, PT, and relationship to the study drug administration, and by SOC, PT, and severity. In addition, the incidence of serious TEAEs and TEAEs leading to discontinuation of study drug will be presented by SOC and PT.

Descriptive statistics for clinical laboratory test results, and vital signs, and for changes from Baseline, will be presented by time point. Baseline is defined as the measurement closest to, but prior to, the administration of study drug. Incidences of potentially clinically significant clinical laboratory results, and vital signs, as defined in the SAP, will also be summarized by time point. A summary of abnormal physical examination findings will also be presented.

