### 7.3. Handling of Missing Data

- Unless otherwise specified, missing values for individual data points will remain as missing. Missing values will not be imputed and only observed values will be used in data analyses and presentations.
- For efficacy analyses, examining the number of participants with 30%, 50%, or 75% improvement in VAS, participants with missing data will be included in the analysis as participants who have not met the criteria for improvement.
- In all other cases, where individual data points are missing, categorical data will be summarized based on reduced denominators (ie, only participants with available data will be included in the denominators).
- Any partial dates will be presented using the CDISC standard ISO.8601 date format as shown in the SDTMIG v3.3 Section 4.4.2.

- All AEs with partial or missing dates and times will be considered treatmentemergent unless a partial start date indicates the AE began before the start of study medication or a stop date indicates the AE ended before the start of study medication.
  - For determination of treatment emergent AEs with partial start dates using the definition above, if the non-missing portion of the partial date is the same as the start of treatment or after (ex: same or later month and year), then it will be considered treatment emergent.

Ex: If treatment begins March 12th, 2022 and an AE has a partial start date of March 2022 (missing day), it will be considered treatment emergent.

- All medications with partial or missing dates recorded on the concomitant medication eCRF will be considered concomitant unless a partial stop date clearly indicates it was stopped before the first dose of study treatment.
  - For determination of concomitant medications with partial stop dates using the definition above, if the missing part of the partial date is the same (same month or year) as the start of treatment or earlier, then it will be considered treatment emergent.

Ex: If treatment begins March 12th, 2022 and a medication has a partial stop date of March 2022 (missing day), it will be considered concomitant.

	-
	-
	_

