#### 10.14.1. Adverse Events

AEs will be coded to system organ class (SOC) and preferred term according to MedDRA, version 24.1. Pretreatment AEs are defined as AEs that have an onset on or after the date the informed consent was signed but before the date of the first dose of study drug. Treatment-emergent adverse events (TEAEs) are defined as AEs that start or worsen after the first dose of study drug. Adverse event severity will be graded using CTCAE v5.0.

Summaries will be provided for TEAEs, with the number and percentage of participants reporting each type of event presented. If a participant reports the same preferred term more than once, it is counted only once within that category. Similarly, if a participant has AEs of two or more preferred terms under the same SOC, then that participant only counts once for that SOC. Furthermore, for a given summary, the preferred term will only be counted once at its worst severity and strongest relationship to study drug.

AEs of special interest will be identified programmatically and reviewed by the study team prior to unblinding. AEs of special interest include:

- (Unexplained) fever
- Grade 2+ allergic, cytokine release, or infusion-related reactions Therapy or infusion interruption indicated but responds promptly to either:
  - symptomatic treatment (e.g., antihistamines, NSAIDS, narcotics, IV fluids)
  - prophylactic medications indicated for  $\leq$ 24 hours
- Grade 2+ injection site reactions
- Grade 2+ neutropenia

The following summaries and listings for AEs will be provided:

- An overall summary table of AEs summarizing the number and percent of participants, in the following categories: any AE, any TEAE, TEAEs by highest severity grade, any TEAEs of special interest, TEAEs by relationship to study drug (related, not related), any serious TEAE, TEAEs leading to drug withdrawal, and TEAEs leading to premature withdrawal from the study, any TEAEs with a fatal outcome
- Incidence of TEAEs by MedDRA SOC and preferred terms
- Incidence of TEAEs by MedDRA SOC, preferred terms, and maximum severity grade
- Incidence of TEAEs by MedDRA SOC, preferred terms, and relationship to study drug.

- Incidence of TEAES of special interest, by SOC, preferred terms, and maximum severity grade.
- Incidence of SAEs by SOC, preferred terms, and maximum severity grade
- Listing of all AEs (with non-treatment-emergent events flagged and AEs of special interest highlighted).
- Listing of all AEs of special interest

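### Unlike the protocol, the SAP's treatment-emergent definition does not cover onset during the first dose, and a timed Day 0 event before or during that dose falls in no class

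*SAP*

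**What the plan says.** The protocol gives the rule twice, with the same boundary. Section 14.4 reads: "A treatment-emergent adverse event (TEAE) is defined as an AE that occurs during or after study drug administration". Section 10.2 says the same of all AEs and SAEs.

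SAP 10.14.1 puts it differently: "Treatment-emergent adverse events (TEAEs) are defined as AEs that start or worsen after the first dose of study drug". It describes pretreatment AEs as those with "onset on or after the date the informed consent was signed but before the date of the first dose of study drug". The first boundary is the dose; the second is a calendar date. The departures table in SAP 11 has rows for laboratory summaries, physical examinations and SF-12 norms, and none for the TEAE definition.

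Three other provisions bear on the point:

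- SAP 7.3 sets the default for incomplete records: "All AEs with partial or missing dates and times will be considered" treatment-emergent. The exceptions are a partial start date or a stop date showing that the event began or ended before study medication started.
- Protocol 9.3 has the site, on Day 0 before dosing, "Record any new AEs since Screening".
- Protocol 10.2 lists a date of onset among the AE items and names no time of onset. Protocol 8.4 does have the injection time recorded.

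**The concern.** Safety and tolerability is the primary objective, and the TEAE tables are its main summary. Two governing documents draw the lower edge of the TEAE class in different places, and the SAP does not acknowledge it.

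The interval in question is not empty. SAP 10.9 describes one dose as two injections given bilaterally, so a reaction after the first joint is injected and before the second begins before the dose is complete. One special-interest category, in Protocol 10.7.1 and SAP 10.14.1, concerns reactions for which interrupting therapy is indicated, which suggests onset while the product is being given. The special-interest incidence table is restricted to TEAEs, so a literal programmer could leave out an event that the table is meant to show.

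Because the two SAP classes are bounded by different things, they are also not complementary. How a Day 0 event is classed then depends on whether someone entered a time.

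**Working it through.** The plan gives no figure on this point to reproduce. The check is to place each possible onset around the first dose under both sets of definitions. Inputs: SAP 10.14.1 and 7.3; Protocol 10.2 and 14.4.

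| Onset | SAP, read literally | Protocol | Result |
|---|---|---|---|
| After consent, before the Day 0 date | Pretreatment | Not a TEAE | Agree |
| Day 0, timed before the dose | Neither class, unless it later worsens | Not a TEAE | Gap in labelling |
| Day 0, timed during the first dose | Neither class | TEAE | Conflict |
| Day 0, timed after the dose | TEAE | TEAE | Agree |
| Day 0, no time recorded | TEAE under 7.3 | TEAE only if onset was during or after dosing | Pre-dose events also counted |
| During the Day 90 dose | TEAE, being after the first dose | TEAE | Agree |

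The third row depends on two conditions: an onset time is recorded, and onset after the first dose is taken to mean after that dose is completed. If it is taken to mean after the dose has started, the conflict in that row disappears. The second row remains a gap on either reading.

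The fifth row assumes that SAP 7.3 covers a record with a full date but no time, which is the natural reading of its reference to missing times. A reaction during the injection is then kept. A pre-dose Day 0 event is kept too, because a Day 0 date without a time does not show that it began or ended before study medication.

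Size. Both documents plan 24 participants per group. One participant is 1/24 = 0.0417, or 4.2 percentage points. SAP 10.14.1 counts participants, not events, so an arm's overall TEAE incidence moves by this amount only if the affected participant has no other TEAE during follow-up.

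**The case against.** The strongest reply is that the harm may never occur. The protocol names only a date of onset. If the eCRF holds only a date, SAP 7.3 keeps every reaction during the first injection in the tables, and the remaining error is over-counting of pre-dose events, which is conservative for safety. SAP 7.3 also uses the start of study medication as its boundary, which suggests that the authors meant the same thing as the protocol. This carries weight, but 7.3 governs incomplete records only. The general definition in 10.14.1 still says something else, and the SAP, which has a tie rule for baseline values recorded at the exact dose time (7.1.1), has none for AEs.

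A second reply is that the events are not hidden. SAP 10.14.1 includes an any-AE row, a listing of all AEs with non-treatment-emergent ones flagged, a listing of all special-interest AEs, and an SAE incidence table not worded as TEAE-only. SAP 10.14.3 summarises injection-site signs by visit. This stands and limits the consequence.

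A third is that the SAP is not simply narrower: it adds worsening, which neither protocol definition mentions. That is correct.

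A reader might infer that reactions during the first injection will drop out of the TEAE tables. The documents do not establish this; it needs both conditions set out in the working. A reader might also infer that a comparison of first and second injections would be distorted, since events during the Day 90 dose always count. No such comparison is planned in the visible text.

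**Conclusion.** The point holds as an inconsistency between protocol and SAP, together with a gap between the SAP's two classes. A timed Day 0 AE before or during the first dose is in neither class. If it began during the dose, the protocol counts it and the SAP, read literally, does not. Without a time, the SAP counts both that event and pre-dose Day 0 events.

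The size is unknown. The documents do not say whether AE onset time is collected, whether the recorded injection time marks the start or the end of the procedure, or how often such events occur. The 4.2 points per participant is conditional on 24 per arm and on no other TEAE in that participant; it is not a general effect of each misclassified event. For pre-dose events with a recorded time, the gap affects only the label, since neither document puts them in the TEAE tables.

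This is worth correcting because the rule underlies the main tables for the primary objective and the correction is nearly free. It does not show that those tables would be wrong.

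**What to change.** In SAP 10.14.1:

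1. Define a TEAE as an AE with onset or worsening at or after the start of the first study-drug administration.
2. Define a pretreatment AE as one with onset after consent and before that same point, so that the two classes are complementary.
3. State that a Day 0 AE without an onset time is treatment-emergent under SAP 7.3 unless the record shows that onset was before dosing, for example because the site entered it at the pre-dose check in Protocol 9.3.

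The cost is three sentences of SAP text and the matching derivation. The downside is that the TEAE count may rise slightly. No new eCRF field is needed: the SAP is Version 3.0, dated October 2023, and a field added then could not capture onset time prospectively for participants already dosed.

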# 8.2. Investigational Product Administration

Investigational product (XT-150 or placebo) will be administered as two bolus, bilateral intraarticular injections into the facet joint. The injection will be performed with fluoroscopic guidance.

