# 10.7. Adverse Events of Special Interest

#### 10.7.1. Adverse Events of Noted Interest in IL-10 Protein Trials

Safety will include the following reported IL-10 protein-associated toxicities as defined by CTCAE (v5.0). Systemic levels of XT 150 produced IL-10 protein are expected to be more than 1000-fold lower than when given as a protein solution (Huhn, 1997); and XT-150 will be predominately localized to the facet joint space.

• Grade 1 (unexplained) fever – 38.6°C to 39°C

- Grade 2 allergic, cytokine release, or infusion-related reactions Therapy or infusion interruption indicated but responds promptly to symptomatic treatment (e.g., antihistamines, NSAIDS, narcotics, IV fluids); prophylactic medications indicated for <24 hours
- Grade 2 injection site reaction Pain; lipodystrophy; edema; phlebitis
- Grade 2 neutropenia <1500 to 1000/mm3; <1.5 to 1.0 x109/L

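### The SAP's Grade 2+ special-interest category for allergic, cytokine-release and infusion-related reactions keeps a prompt-response clause written for Grade 2, so read literally it leaves out non-responding and fatal reactions

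*SAP*

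**What the plan says.** Protocol 10.7.1 lists toxicities of interest at a single grade each. Unexplained fever is listed at Grade 1 with a fixed temperature range. The others are at Grade 2, among them "Grade 2 allergic, cytokine release, or infusion-related reactions Therapy or infusion interruption indicated but responds promptly to symptomatic treatment" or a need for prophylaxis of less than 24 hours, and "Grade 2 neutropenia <1500 to 1000/mm3".

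SAP 10.14.1 restates the list with open-ended grades. Its reaction bullet reads "Grade 2+ allergic, cytokine release, or infusion-related reactions Therapy or infusion interruption indicated but responds promptly to either", followed by two sub-bullets: symptomatic treatment, or prophylactic medication for up to and including 24 hours. The next bullet is simply "Grade 2+ injection site reactions", and the neutropenia bullet likewise gives only Grade 2+. The fever bullet gives no grade.

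On selection, the SAP states: "AEs of special interest will be identified programmatically and reviewed by the study team prior to unblinding". The category feeds four outputs in the same section:

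- the special-interest line of the overall AE summary
- the table described as "Incidence of TEAES of special interest, by SOC, preferred terms, and maximum severity grade"
- the special-interest listing
- the highlighting of special-interest events in the listing of all AEs.

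The SAP's table of departures from the protocol (Section 11) covers laboratory summaries, physical examinations and SF-12 norms. It does not mention the special-interest list.

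**The concern.** In the protocol the clause describes a Grade 2 reaction, one that calls for interruption but settles quickly. That description does not carry over to higher grades. Attached to Grade 2+, it can work as an entry test that a reaction fails by being prolonged, refractory or fatal.

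Safety and tolerability are the primary objective (Protocol 5.1.1, SAP 4.1). A special-interest table broken down by maximum grade is meant to bring the worst reactions forward. If its entry rule screens out those that did not respond, an arm could show no reaction of this kind in the special-interest outputs while the general AE tables contain one.

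**Working it through.** No figure in the plan bears on this point, so the check is a comparison of wording followed by an enumeration.

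**Step 1. The two wordings side by side.**

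| Feature | Protocol 10.7.1 | SAP 10.14.1 |
|---|---|---|
| Grade of reaction | 2 | 2 or higher |
| Prompt-response clause | follows the Grade 2 label as its description | kept, and set out with the word either and two sub-bullets |
| Prophylaxis limit | less than 24 hours | 24 hours or less |
| Descriptors on injection-site and neutropenia items | present | removed |

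For the two neighbouring items the SAP raised the grade and dropped the descriptor. Here it raised the grade, kept the descriptor and gave it the layout of a criterion.

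**Step 2. Enumerate grade against response.** Assume that interruption was indicated, and take each text literally.

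| Reaction | SAP as written | Protocol as written | SAP without the clause |
|---|---|---|---|
| Grade 2, prompt response | in | in | in |
| Grade 2, no prompt response | out | out | in |
| Grade 3 or 4, prompt response | in | out | in |
| Grade 3 or 4, no prompt response | out | out | in |
| Grade 5 (fatal) | out | out | in |

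A fatal reaction is out because it cannot have responded promptly. The literal SAP rule therefore drops three rows that its own Grade 2+ threshold would admit.

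**Step 3. Can a program apply the clause?** Protocol 10.2 lists the recorded AE items: term, onset date, date of resolution or stabilization, severity, relationship, and action taken with study medication. Grade and reaction type can be taken from severity and term. None of the listed items records promptness of response or length of prophylaxis, and neither document defines prompt. The reference to an infusion also fits poorly with a product "administered as two bolus, bilateral intraarticular injections into the facet joint" (Protocol 8.2). A programmer would have to ignore the clause or devise a proxy, and the SAP does not say which.

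**Step 4. Size, as an illustration.** Take 24 treated participants in an arm (72/3) and one reaction that fails the clause. Without the clause the row shows 1/24 = 4.2%. The exact (Clopper-Pearson) 95% interval has these limits:

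- lower: 1 − 0.975^(1/24) = 0.0011, or 0.1%
- upper: the p solving (1−p)^24 + 24p(1−p)^23 = 0.025, which is p = 0.211, or 21.1%.

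With the clause applied literally, the row shows 0/24. The documents give no expected rate for such reactions, so this shows what one event would do and predicts nothing. The SAP plans counts and percentages for AEs, and the interval is added here only for scale.

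**The case against.** The best defence is that the clause is a leftover gloss and not a condition. Grade 2+ suggests that higher grades were meant to be in. In the text as read, dashes and minus signs are missing elsewhere in the SAP (the study-day formula in 7.1.1, the score ranges in 10.13.5), so a dash setting off the description may have been lost here too. The list is introduced as what special-interest events include, which need not be exhaustive, and the study team reviews the selection before unblinding. All of this stands as a reason not to treat exclusion as certain. It does not settle the reading. The word either with sub-bullets favours a criterion, the neighbouring bullets lost their descriptors, and the SAP gives the review no criteria for overriding the program.

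Three stronger readings are tempting and are not supported:

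- **All of the most severe reactions are excluded.** They are not. A Grade 3 or 4 reaction that responds promptly meets the literal rule.
- **The clause can never be met.** The wording covers interruption of therapy as well as of an infusion, a second dose is planned at Day 90, and action taken with study medication is recorded. Onset and resolution dates are also recorded, as are medications used to treat an SAE (Protocol 10.3). The full CRF is not available here. What the documents support is that the clause cannot readily be programmed.
- **Safety information disappears.** It does not. An excluded event still appears in the TEAE tables by severity and by relationship, in the SAE table and listing if serious, in the listing of all AEs, and in the fatal-outcome line and death listing if fatal.

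**Conclusion.** The point holds as a defect in a reporting definition that should be corrected. Followed literally, SAP 10.14.1 removes non-responding Grade 2 to 4 reactions and fatal reactions from the special-interest row, table, listing and highlighting, against its own stated threshold. The effect is confined to those four outputs. It depends on the clause being applied as a condition and on the review before unblinding not restoring the event. The 1/24 against 0/24 contrast assumes one such event in a fully treated arm of 24 and is illustrative only.

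Separately, the SAP and protocol lists differ in grade, and SAP Section 11 does not record this.

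**What to change.** In SAP 10.14.1, end the bullet after the Grade 2+ threshold and the three reaction types. Delete everything from the mention of interruption through the two sub-bullets. The category then has the same form as the injection-site and neutropenia bullets and can be selected from the recorded term and severity.

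Add a row to the departures table in SAP Section 11 stating that the special-interest list uses open-ended grades where Protocol 10.7.1 gives single grades.

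A protocol amendment is not needed for this alone. If the protocol is amended for other reasons, reconcile the whole 10.7.1 list, including its response clause and its fixed fever and neutropenia ranges. Changing only the grade words there would recreate the same combination and leave bounded ranges beside open-ended grades.

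The cost is a wording change and one table row, documented as a SAP amendment before database lock as SAP Section 2 provides. It needs no new data, simplifies programming, and changes no treatment or management rule. An optional protocol change would need sponsor approval and then IRB approval (Protocol 15.1, 17.2).
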